Rationale for change	Based on benefit-risk change after 1280-022 primary endpoint analysis results
Section to be changed	5.4.2 Methods of sample collection
Description of change	Blood for PK and ADA is no longer collected
Rationale for change	Based on benefit-risk change after 1280-022 primary endpoint analysis results
Section to be changed	5.5 Assessment of biomarker(s)
Description of change	biomarkers samples are no longer collected
Rationale for change	Based on benefit-risk change after 1280-022 primary endpoint analysis results
Section to be changed	5.6.1 Assessment of Immunogenicity
Description of change	blood samples for immunogenicity assessments are no longer collected
Rationale for change	Based on benefit-risk change after 1280-022 primary endpoint analysis results
Section to be changed	6.2.2.3 Cohorts D1, D2 and F
Description of change	Reference to reduced flow chart
Rationale for change	To be consistent with the revised flowcharts for cohorts D1, D2 and F
Section to be changed	6.2.3.1 End of treatment visit
Description of change	Sample collection details removed
Rationale for change	To be consistent with flowchart revision
Section to be changed	7.3 Planned analysis

Proprietary confidential information © 2024 Boehringer Ingelheim International GmbH or one or more of its affiliated companies

Description of change	Final analysis timepoint description removed
Rationale for change	To conduct final analyses before last patient out
Section to be changed	10.2.3 FLOW CHART for PK, immunogenicity, and biomarkers for cohort F
Description of change	Blood samples no longer collected
Rationale for change	To be consistent with the revised flowchart for cohort F
Section to be changed	10.2.4 FLOW CHART for PK, immunogenicity, and biomarkers for cohorts D1 and D2
Description of change	Blood samples no longer collected
Rationale for change	To be consistent with the revised flowchart for cohorts D1 and D2

2 LIST OF ABBREVIATIONS

Term	Definition / description
AE	Adverse Event
AESI	Adverse Event of Special Interest
ALT	Alanine Aminotransferase
AST	Aspartate Transaminase
BI	Boehringer Ingelheim
CR	Complete response
COVID-19	Coronavirus Disease 2019
CTL	Clinical Trial Leader
DC	Disease control
ECG	Electrocardiogram
FDA	Food and Drug Administration
ICH	International Conference on Harmonisation
IPD	Important Protocol Deviation
ITT	Intent-to-Treat
KM	Kaplan-Meier
LLT	Lowest Level Term
MedDRA	Medical Dictionary for Regulatory Activities
MQRM	Medical Quality Review Meeting
MRI	Magnetic Resonance Imaging
MTD	Maximum Tolerated Dose
OR	Objective response
OS	Overall Survival
PD	Progressive Disease
PD	Protocol Deviation
PFS	Progression Free Survival
PK	Pharmacokinetics
PR	Partial response
RP2D	Recommended Phase II Dose
RS	Randomised Set
SAE	Serious Adverse Event

Proprietary confidential information © 2021 Boehringer Ingelheim International GmbH or one or more of its affiliated companies

Term	Definition / description
SD	Stable Disease
SDL	Subject Data Listings
SIR	Synoptic Interim Report
SOC	System Organ Class
SOP	Standard Operating Procedure
TSAP	Trial Statistical Analysis Plan

3 INTRODUCTION

As per ICH E9, the purpose of this document is to provide a more technical and detailed elaboration of the principal features of the analysis described in the protocol, and to include detailed procedures for executing the statistical analysis of the primary and secondary variables and other data.

This TSAP assumes familiarity with the Clinical Trial Protocol (CTP), including Protocol Amendments. In particular, the TSAP is based on the planned analysis specification as written in CTP (see in section “Statistical Methods and Determination of Sample Size”). Therefore, TSAP readers may consult the CTP for more background information on the study, e.g., on study objectives, study design and population, treatments, definition of measurements and variables, planning of sample size, randomisation. This TSAP follows Boehringer Ingelheims (BI) internal reference ([1](#)).

The trial consists of three parts. Part 1 includes a dose finding cohort A and part 2 includes three dose finding cohorts B, C and D and one expansion cohort E. Part 3 includes cohort D1, D2 and F.

The TSAP describes the analysis for all the cohorts of the trial. After each of dose finding cohort (cohorts A, B, C and D), safety analyses were performed and documented.(see [Section 9.1](#)).

SAS Version 9.4 or later version will be used for all analyses unless otherwise specified.

4 CHANGE IN THE PLANNED ANALYSIS OF THE STUDY

4.1 ADDITIONS/NEW ANALYSES

The following additions/new analyses to the statistical methods described in the CTP and subsequent amendments are detailed in this TSAP:

- Where considered appropriate, the potential impact of Coronavirus Disease 2019 (COVID-19) on the study will be assessed by producing additional summaries of disposition, protocol deviations, treatment exposure and adverse events (AEs). The start date for COVID-19 having an impact on the trial will be taken as the earliest date of a COVID-19 related protocol deviation, discontinuation due to COVID-19, onset of a severe acute respiratory syndrome coronavirus 2 (SARS-CoV-2) related AE or COVID-19 related global BI recruitment hold (17 MAR 20).

4.2 CHANGES

Not applicable.

4.3 CLARIFICATIONS

The following points warrant further clarification:

- The terms “progression”, “progressive disease” (PD) and “disease progression” will be used interchangeably within this document.
- The terms “treatment cycle” or “treatment course” will be used interchangeably throughout this document.
- The terms “study medication” and “trial medication” will be used interchangeably throughout this document.
- If not stated otherwise, date of randomisation will be replaced by first treatment administration of any study medication in the outputs (i.e. including the run-in period)

5 ENDPOINTS

5.1 PRIMARY ENDPOINTS

5.1.1 Cohorts A, B, C, and D:

The primary endpoint is the maximum tolerated dose (MTD) of trial medications based on the occurrence of dose limiting toxicity (DLT) during the first treatment course. The planned treatment course consists of 28 days.

MTD:

The MTD is defined as the highest dose with less than 25% risk of the true DLT rate being above 33%. The MTD evaluation period is defined as the time from the first administration of any study medication up to start of cycle 2. That means that the exact duration of this period will be derived for each patient. If the patient experiences any delay after planned 28 days of cycle 1 but prior to the start of cycle 2, this delay will be also considered as MTD evaluation period.

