If DLTs are observed in the first two consecutive patients of a previously untested dose level, subsequent enrolment to that dose-level cohort will be stopped. The BLRM will then be re-run to confirm that the dose level still fulfils the EWOC principle. Based on this information, the SC will evaluate whether the next patients will be enrolled at the same dose level, or if they will be enrolled at a lower dose level.

After all patients in the initial dose-level cohort have either experienced a DLT or have been observed for at least one course (28 days) without experiencing a DLT, the Bayesian model will be updated with the newly accumulated data. The SC will then determine the dose regimen for the next dose-level cohort, based on the available toxicity information (including DLTs, AEs that are not DLTs, and AE information post-cycle 1), recommendations from the BLRM, and other data (e.g. anti-tumour activity, pharmacokinetics) if applicable. Details on the Bayesian design are provided in [Sections 7.1](#) and [Appendix 10.6](#).

The overdose risk will be calculated for each further dose combination, and patient enrolment into dose levels will be permitted to all dose combinations which fulfil the escalation with overdose control (EWOC) criterion. Based on the Bayesian model and the additional information as defined above, the SC will decide on the next dose level to be investigated. In the SC meeting, data for each patient in the current dose-level cohort will be described in detail, updated safety data on other ongoing patients, including data in later courses, will be discussed as well.

The SC must reach a consensus on whether to de-escalate, re-escalate and/or expand recruitment into particular cohorts, or to declare the MTD₁/RP2D₁. BI will prepare minutes from the SC meetings and circulate them to each Investigator.

To further assess the safety (e.g. specific suspected treatment-related adverse events) of xentuzumab in combination with abemaciclib, one or several doses that are considered acceptably safe, i.e. shown to be lower than or equal to any potential MTD, may be explored to determine the RP2D₁. Nevertheless, a minimum of 6 evaluable patients need to be treated at the MTD₁/RP2D₁ in the dose finding cohort A prior to starting part 2 (cohorts B, C, D and E) and any dose declared as MTD₁/RP2D₁ by the SC needs to fulfil the escalation with overdose control (EWOC) criteria.

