5. VARIABLES AND THEIR ASSESSMENT

5.1 TRIAL ENDPOINTS

5.1.1 Primary Endpoint(s)

For dose finding cohorts A, B, C, and D (dose finding):

The primary endpoints for each dose finding cohort are the MTD and the number of patients with dose limiting toxicities (DLT) in the MTD evaluation period.

The MTD evaluation period is defined as the first treatment cycle (28 days). The MTD is defined as the highest dose with less than 25% risk of the true DLT rate being above 33%. For definition of DLTs, refer to [Section 5.3.7](#)

A Bayesian Logistic Regression Model (BLRM) employing the escalation with overdose control (EWOC) principle will be used during each dose finding cohort for a selection of doses to investigate and for estimation of the MTD. Cohorts of patients will receive xentuzumab and abemaciclib (with or without endocrine therapy) until the MTD is reached or until the Steering Committee (SC) decides on stopping the dose finding. Each dose-level cohort will consist of newly enrolled patients. Estimation of the MTD during each dose finding cohort of the study will be based upon the estimation of the probability of a DLT in the MTD evaluation period in the set of evaluable patients for MTD. The corresponding methodology is described in [Section 7](#).

The MTD estimate established during the dose finding cohort will be re-investigated after the corresponding expansion cohort by re-running the BLM including all data from dose finding cohort and expansion cohort, in particular also considering the DLT information from all treatment cycles.

For expansion cohort E

The primary endpoint for expansion part is objective response (OR) defined as best overall response of complete response (CR) or partial response (PR), where best overall response is determined according to Response Evaluation Criteria In Solid Tumours (RECIST) version 1.1 from date of first treatment administration (including run-in for cohort E) until the earliest of disease progression, death or last evaluable tumour assessment before start of subsequent anti-cancer therapy.

For expansion cohorts D1 and D2:

The primary endpoint for expansion part is PFS rate at 18 month defined as the rate of absence of disease progression or death at 18th month, where progression is determined according to Response Evaluation Criteria In Solid Tumours (RECIST) version 1.1.

For expansion cohort F

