5.3.7 Dose Limiting Toxicities (DLTs)

A dose limiting toxicity (DLT) in this study is defined as an adverse event or laboratory abnormality which 1) is considered related, probably related or possibly related to study drug and 2) meets any of the following criteria, unless that toxicity can be clearly attributed to cancer progression or to another clearly identified etiology:

- CTCAE Grade 3 hyperglycaemia lasting > 48 hours
- CTCAE Grade 4 hyperglycaemia
- CTCAE Grade ≥ 3 pneumonitis
- CTCAE Grade ≥ 3 febrile neutropenia
- CTCAE Grade 4 hematologic toxicity lasting longer than 5 days
- CTCAE Grade 4 thrombocytopenia of any duration and Grade 3 thrombocytopenia associated with bleeding
- AST or ALT $> 5x$ ULN (for baseline AST/ALT \leq ULN) or $>$ (baseline value + 4x ULN) (for baseline AST/ALT $>$ ULN)
- CTCAE Grade ≥ 3 diarrhoea, nausea, or vomiting lasting more than 2 days despite maximal supportive care
- CTCAE Grade ≥ 3 skin rash despite adequate supportive care measures
- CTCAE Grade ≥ 3 fatigue/asthenia lasting for more than seven days
- Grades 3 to 4 hyperlipidaemia (total cholesterol > 400 mg/dL or triglycerides > 500 mg/dL) not improving despite appropriate treatment for 2 weeks

Proprietary confidential information © 2024 Boehringer Ingelheim International GmbH or one or more of its affiliated companies

- Any AE necessitating a 2-week treatment interruption (except for hematologic AEs)
- All other non-hematologic toxicities of CTCAE Grade ≥ 3 (except alopecia, infusion-related reaction and those mentioned above)
- Any other study drug related toxicity considered significant enough to be qualified as DLT in the opinion of the investigators, and confirmed by the safety review with the BI clinical monitor and BI project physician (TMM), will be reported as a DLT

For the purposes of dose finding, only DLT events that occur during the first treatment period of 28 days will be considered. Decisions regarding dose escalation/de-escalation steps will be made only after discussion between the sponsor and the investigators, and in consideration of all the available safety information. Available data of DLTs occurring after first treatment course and all unusual/unexpected AE at any time during treatment will be considered for the purpose of recommending the dose for cohorts B, C, D (dose finding), E, F, D1 and D2.

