$$r_{d1,d2} \sim \text{Binomial}(n_{d1,d2}, \pi_{12,d1,d2})$$

where $r_{d1,d2}$ denotes the random variable describing the observed number of DLTs in $n_{d1,d2}$ patients at the dose combination d_1, d_2 .

Since a Bayesian approach is applied, prior distributions f for each of the parameter vectors $\theta_1=(\log(\alpha_1),\log(\beta_1))$, $\theta_2=(\log(\alpha_2),\log(\beta_2))$ and for the interaction term η need to be specified.

The prior distributions for θ_k will be specified as a mixture of two bivariate normal distributions,

$$f(\theta_k) = a_{1,k} f_1(\theta_k) + a_{2,k} f_2(\theta_k)$$

with

$a_{1,k}$, $a_{2,k}$ the prior mixture weights ($a_{1,k} + a_{2,k} = 1$), $k = 1,2$ and

$f_i(\theta_k) = \text{MVN}(\mu_{ik}, \Sigma_{ik})$ a bivariate normal distribution with mean vector μ_{ik} and covariance matrix Σ_{ik} where

$$\Sigma_{ik} = \begin{pmatrix} \sigma_{ik,11}^2 & \sigma_{ik,11}\sigma_{ik,22}\rho_{ik} \\ \sigma_{ik,11}\sigma_{ik,22}\rho_{ik} & \sigma_{ik,22}^2 \end{pmatrix}$$

Mixture prior distributions have the advantage that they allow for specification of different logistic dose-toxicity curves, therefore making the prior more robust.

A weakly informative normal prior distribution will be used for η .

The estimated probability of DLT $\pi_{12,d1,d2}$ at each dose combination d_1, d_2 from the model will be summarized using the following intervals:

- * Under dosing: [0.00, 0.16)
- * Targeted toxicity: [0.16, 0.33)
- * Over dosing: [0.33, 1.00]

The BLRM recommended dose combination for the next cohort is the combination with the highest posterior probability of the DLT rate falling in the target interval [0.16, 0.33) among the dose combinations fulfilling the EWOC principle. Per EWOC it should be unlikely (<25% posterior probability) that the DLT rate at the dose combination will exceed 0.33. However, the maximum allowable dose increment for the subsequent cohort will be no more than 100 % for each drug.

The MTD may be considered reached if one of the following criteria is fulfilled:

1. The posterior probability of the true DLT rate in the target interval [0.16 – 0.33) of the MTD is above 0.50, or
2. At least 6 patients have been treated at the MTD.

Prior derivation

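### SAP 5.1.1 lets the MTD evaluation period run to the start of cycle 2, while the protocol fixes it at 28 days, and the SAP declares no change

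*SAP*

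**What the plan says.** The protocol gives one fixed window. Section 5.1.1 states "The MTD evaluation period is defined as the first treatment cycle (28 days"), and section 5.3.7 says that for dose finding "only DLT events that occur during the first treatment period of 28 days will be considered". Section 4.1.2.1 times the model update to match: each patient in the initial dose-level cohort must have had a DLT or "have been observed for at least one course (28 days) without experiencing a DLT".

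The SAP gives a different window. Section 5.1.1 states "The MTD evaluation period is defined as the time from the first administration of any study medication up to start of cycle 2". It derives the length separately for each patient and says of a delay after day 28 that "this delay will be also considered as MTD evaluation period". SAP 7.4.1 refers back to this definition for the DLTs that determine the MTD and for the posterior probabilities to be displayed.

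The entry in SAP 4.2, where changes from the protocol belong, is "Not applicable". The clarifications in SAP 4.3 do not mention the window either. SAP version 2.0 is dated 25 October 2021. The protocol revision of 4 March 2022 is later and still says 28 days.

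**The concern.** The two documents define the primary endpoint of cohorts A, B, C and D differently. Take a first DLT on day 35. Under the protocol it is outside the window for every patient. Under the SAP it is inside if cycle 2 has not yet started and outside if cycle 2 started on day 29. The BLRM in protocol 7.1 treats the number of patients with a DLT as binomial and makes no allowance for unequal observation time, so it assumes that each patient was observed for the same period.

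The SAP wording is also incomplete. It sets no end of the window for a patient who never starts cycle 2. It does not say whether the start of cycle 2 means the calendar visit or the actual resumption of dosing.

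At stake is whether the reported MTD rests on the rule in the protocol. The overdose limit is a sharp threshold: "it should be unlikely (<25% posterior probability) that the DLT rate at the dose combination will exceed 0.33". A single reclassified patient could move a dose across it.

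**Working it through.** **Inputs**
- Model: protocol 7.1, with reference doses of 1000 mg xentuzumab weekly and 150 mg abemaciclib every 12 hours.
- Prior: Table 7.1:3 (cohort A), as mean vector, SDs, correlation.
  - Xentuzumab (log α₁, log β₁): weight 0.9 on (−3.697, −0.517), (1.031, 0.816), 0.034; weight 0.1 on (−4, −0.5), (2, 1), 0.
  - Abemaciclib (log α₂, log β₂): weight 0.9 on (−2.515, 0.898), (0.829, 0.808), −0.510; weight 0.1 on (−3, 0.9), (2, 1), 0.
  - Interaction η: normal, mean 0, SD 0.707.
- Overdose limit: P(DLT rate ≥ 0.33) below 0.25.
- Size: one of the two alternative MTD criteria in protocol 7.1 is "At least 6 patients have been treated at the MTD".

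**Formula**

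At 1000/150 both doses equal their reference values, so the slope terms vanish:
- π₁ = α₁/(1 + α₁) and π₂ = α₂/(1 + α₂)
- π⁰ = π₁ + π₂ − π₁π₂
- odds(π) = odds(π⁰) × exp(η)

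For r DLTs in n patients, each of 4 million prior draws gets a weight proportional to π^r (1 − π)^(n − r). P(overdose) is the total normalised weight of draws with π ≥ 0.33.

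**Reproducing the plan's own figures** (Table 10.6:1, P(overdose) at 1000/150)

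| DLTs/patients | Protocol | Recomputed |
|---|---|---|
| 0/3 | 0.027 | 0.026 |
| 1/3 | 0.141 | 0.144 |
| 2/3 | 0.430 | 0.426 |
| 0/6 | 0.009 | 0.008 |
| 1/6 | 0.048 | 0.050 |

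The largest difference is 0.004. The recommended next dose matches in all seven scenarios of that table.

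**Effect of one additional DLT at 1000/150**

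| Change | P(overdose) | Crosses 0.25? |
|---|---|---|
| 0/6 to 1/6 | 0.008 to 0.050 | no |
| 1/6 to 2/6 | 0.050 to 0.183 | no |
| 2/6 to 3/6 | 0.183 to 0.427 | yes |
| 3/9 to 4/9 | 0.213 to 0.432 | yes |
| 3/12 to 4/12 | 0.098 to 0.237 | no |
| 4/12 to 5/12 | 0.237 to 0.438 | yes |

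With the fixed window, 2 DLTs in 6 patients pass whenever cycle 2 starts. With the SAP window, a first DLT after day 28 in one of the other four patients, if that patient's cycle 2 is late, makes it 3 in 6 and the same dose fails.

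**How often the count sits at that margin**

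At the prior mean DLT rate of 0.150 (Table 7.1:4), the binomial probability of exactly 2 in 6 is 15 × 0.150² × 0.850⁴ = 15 × 0.0225 × 0.522 = 0.18. A late first DLT in a delayed patient must then occur as well. The documents give no figure for that.

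**The case against.** The strongest reply is that this is a wording difference with little practical reach, and much of it stands.

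- **Delays should be short.** Visit dates are counted from C1V1 (flow charts; protocol 6.2.2), missed visits are not rescheduled, and a missed xentuzumab infusion is not made up (protocol 4.1.4.1). A pause in treatment does not by itself move cycle 2. The SAP nevertheless provides for a delay, so some extension is possible.
- **Many delayed patients cannot change the count.** The outcome is one yes or no per patient, so a patient delayed by a DLT is already counted. Only a patient delayed without one matters. Table 4.1.4.2:2 requires abemaciclib suspension for Grade 3 haematologic toxicity, which is not in general a DLT under section 5.3.7, so such a patient can exist.
- **The direction is cautious.** A delay can add DLTs but not remove them, so it lowers the MTD or leaves it unchanged.
- **Late events already have a place.** The Steering Committee weighs adverse events after cycle 1 (4.1.2.1), later DLTs inform the recommended doses (5.3.7), and a model re-run using all cycles is planned after the corresponding expansion cohort (5.1.1). This limits the harm, but it also means that late DLTs need not enter the primary window for some patients only.
- **The figures are limited.** They use the cohort A prior, and protocol 7.1 says that the priors for B, C and D also draw on data from this trial. The three-patient figures do not bear on a declared MTD in cohort A, where 4.1.2.1 requires at least 6 evaluable patients.
- **A hard cut at day 28 needs an onset rule.** Several DLT criteria in 5.3.7 depend on duration, so an event that begins in cycle 1 may qualify only after day 28. This is right, and the fix includes such a rule.

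A reader might go further and infer that delays are mainly caused by toxicity, so that the window biases the DLT rate materially upward, or that the final MTD contradicts the decisions that opened later cohorts. The documents support neither. They give no reasons for or counts of delays to cycle 2 and no late DLTs. SAP section 3 says that safety analyses followed each dose-finding cohort, but not that any conflict arose.

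**Conclusion.** The conflict is real and undeclared. It concerns the primary endpoint of four cohorts, and following the SAP as written would apply a different rule from the protocol. The likely effect on the MTD is small and toward caution. It is not nil: with the cohort A prior at 1000/150, one DLT counted only because cycle 2 started late moves P(overdose) from about 0.18 (2/6) to about 0.43 (3/6) and reverses the overdose-control result. At lower counts, such as 1/6 to 2/6, it does not.

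This rests on the published prior, the plain binomial likelihood, and the assumption that at least one patient has a delayed cycle 2 and a first DLT in the gap. How often that occurs cannot be determined from the documents. The point should be corrected for consistency and is not evidence that a declared dose is wrong.

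**What to change.** In SAP 5.1.1 and 7.4.1:
1. Base the primary MTD model on DLTs with onset in days 1 to 28 from first administration, for every patient.
2. State that an event with onset by day 28 counts even if its duration criterion is met later.
3. Report later DLTs in the all-course tabulation that protocol 7.3.4 already plans.
4. Give the start-of-cycle-2 window as a sensitivity analysis. For that analysis, define the start of cycle 2 and say when the window closes for a patient who never reaches it.

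If the sponsor prefers to keep the longer window as primary, it should be declared in SAP 4.2, reconciled with protocol 5.1.1 and 5.3.7, and shown with the 28-day result alongside.

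The cost is a few sentences in the SAP and one additional run of an existing model. No new data are needed beyond the onset dates of DLTs.
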